#### **2.4.5.1 Analyses of Hypoglycemia**

All analyses of hypoglycemia will be performed on the safety population, using events occurring during the on-treatment period (as defined in [Section 2.1.5](#)).

##### ***Incidence of patients with at least one hypoglycemia***

- Incidence of patients with at least one hypoglycemia will be presented by treatment group for any hypoglycemia and for each hypoglycemia category (as described in [Section 2.1.5.1](#)). Non classified hypoglycemia will be displayed.
- For any hypoglycemia, severe and documented symptomatic hypoglycemia category, incidence of patients with at least one hypoglycemia will be compared for the switching arm versus the non-switching arm using a logistic regression method. The model will include fixed-effect terms for treatment group and the randomization stratum of screening HbA1c (<8%, ≥8). If the logistic model does not converge (e.g., due to sparse data), the randomization stratum may be removed from the model. Odds-ratios and 95% CIs will be displayed using forest plots.
- The number (%) of patients with at least one hypoglycemia leading to permanent IMP discontinuation will be provided by treatment group.
- Incidence of patients with at least one severe hypoglycemia with neuroglycopenic symptoms and/or SMPG <2.8 mmol/L (50 mg/dL) will be summarized.
- If the number of patients impacted by COVID-19 is sufficient, the incidence of patients with at least one hypoglycemia (any, severe, documented symptomatic) will also be

presented by subgroup of COVID-19 impact (Non-impacted, Impacted) (see definition [Section 2.2](#)) and compared between treatment groups using a similar logistic regression model as described above, with added fixed-effect terms for the subgroup and the subgroup-by-treatment interaction. Odds-ratios and 95% CIs will be presented across subgroups using forest plots. The significance level of the subgroup-by-treatment interaction will also be provided for descriptive purpose.

#### ***Number and rate of hypoglycemia per patient-year***

- Number and rate of hypoglycemia per patient-year (computed as  $365.25 \times [\text{total number of episodes of hypoglycemia}] / [\text{total number of days exposed}]$ ) will be summarized by treatment group for any hypoglycemia and for each hypoglycemia category (as described in [Section 2.1.5.1](#)). Non classified hypoglycemia will be displayed.
- For any hypoglycemia the cumulative mean number of hypoglycemia per patient will be summarized over time using Nelson-Aalen estimates. Figures will be provided.
- For any hypoglycemia, severe and documented symptomatic hypoglycemia category, number and rate of hypoglycemia per patient-year will be compared for the switching arm versus the non-switching arm using an overdispersed Poisson regression model with a log-link function, and the logarithm of the treatment-emergent period as offset (using PROC GENMOD). The dispersion parameter will be estimated by Pearson's chi-square statistic divided by its degrees of freedom (option SCALE=PEARSON). The model will include fixed-effect terms for treatment group and the randomization stratum of screening HbA1c ( $<8\%$ ,  $\geq 8\%$ ). If a model does not converge (eg, due to sparse data), the randomization stratum may be removed from the model. Rate ratios and 95% CIs will be displayed using forest plots.
- The number of severe hypoglycemia with neuroglycopenic symptoms and/or SMPG  $<2.8$  mmol/L (50 mg/dL) per patient-year of exposure will be summarized by treatment group.

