### 9.4.3 Safety analyses

All safety analyses will be descriptive and performed on the Safety Population.

The **observation period for safety data** is divided into 3 main segments:

- The pre-treatment period is defined as the time from informed consent up to the time of the first injection of IMP.
- The on-treatment period is defined as the time from the first injection of IMP up to 1 day after the last injection of IMP.

- The post-treatment period is defined as the time starting 1 day after last injection of IMP (after the on-treatment period).

The AE observations will be classified per the observation periods of safety data as defined above:

- **Pre-treatment AEs** are AEs that developed or worsened or became serious during the pre-treatment period.
- **Treatment-emergent AEs** are AEs that developed or worsened or became serious during the on-treatment period.
- **Post-treatment AEs** are AEs that developed or worsened or became serious during the post-treatment period.

Analyses will focus on safety observations during the on-treatment period.

The baseline value for safety variables will be defined as the last available value prior to the first injection of IMP.

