**Table 7 - Safety analyses**

Endpoint	Statistical Analysis Methods
Secondary: Number of participants with at least one hypoglycemic event for the 16-week treatment period	Proportions of participants with at least one hypoglycemic event will be presented overall and by type of event for each treatment group.
Secondary: Number of hypoglycemic events per participant-year for the 16-week treatment period	
Incidences of hypoglycemia per participant-year will be computed as: <math>365.25 \times (\text{number of episodes of hypoglycemia}) / (\text{number of days exposed})</math> and summarized overall and by type of event for each treatment group.
 
For exploratory purpose, odds-ratios and rate ratios of hypoglycemic event may be provided for SAR341402/NovoLog switching group versus NovoLog non-switching group, overall and for some categories of hypoglycemia. Details will be provided in the SAP.
 
Further analyses (eg, by subgroup, over time) may be done as appropriate and will be detailed in the SAP.

Secondary: Number of participants with AE for the 16-week treatment period	
All AEs will be coded using the version of MedDRA currently in use by the sponsor at the time of database lock.
 
Adverse event incidence tables will present using the MedDRA hierarchy, the number and percentage of participants experiencing an AE for each treatment group.
 
Adverse event incidence table will be provided by treatment group for all types of TEAEs: all TEAEs, all treatment-emergent SAEs, all TEAEs leading to definitive treatment discontinuation and all TEAEs leading to death.
 
The number and proportion of participants with injection site and hypersensitivity reactions (identified by MedDRA search) will also be summarized by treatment group, and events adjudicated as possible hypersensitivity reactions by the ARAC will be described.

AE: adverse event; MedDRA: Medical Dictionary for Regulatory Activities; SAE: serious adverse event; TEAE: treatment-emergent adverse event

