### ***Safety observation period***

The observation period for safety data will be divided into 3 main segments:

- The **pre-treatment period** is defined as the time from informed consent up to the time of the first injection of IMP.
- The **on-treatment period** is defined as the time from the first injection of IMP up to the last injection of IMP + 1 day (included).
- The **post-treatment period** is defined as the time from the last injection of IMP + 2 days (included).

Analyses will focus on safety observations during the on-treatment period.

The **on-study observation period** is defined as the time from first injection of IMP until the end of the study (defined as the date of end of participation).

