### ***Observation period***

The observation period for exposure is defined as the time from the first injection of IMP up to the day of last injection of IMP.

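### The crude hypoglycaemia rate counts events for one day longer than its denominator, so it is expected to run about 1% high; one person-time should serve both the rate and the Poisson offset

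*SAP*

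**What the plan says.** **Endpoint.** Protocol Table 7 lists "Secondary: Number of hypoglycemic events per participant-year for the 16-week treatment period". Its formula is 365.25 times the number of episodes, divided by the number of days exposed.

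**Events counted.** SAP 2.4.5.1 restricts all hypoglycaemia analyses to the safety population, "using events occurring during the on-treatment period". Under Safety observation period, SAP 2.1.5 says that this period "is defined as the time from the first injection of IMP up to the last injection of IMP + 1 day (included"), and it opens the post-treatment period at the last injection plus 2 days. Protocol 9.4.3 describes the on-treatment period as "the time from the first injection of IMP up to 1 day after the last injection of IMP".

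**Crude denominator.** SAP 2.4.5.1 divides by the "total number of days exposed" and does not define the phrase there. The only exposure definition in the SAP is in 2.4.3.1: "The observation period for exposure is defined as the time from the first injection of IMP up to the day of last injection of IMP". The duration formula that follows is last administration date minus first administration date, plus 1. The same section sums that duration over patients and expresses it in patient-years.

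**Model.** The overdispersed Poisson regression takes as its offset "the logarithm of the treatment-emergent period as offset". The SAP does not define that term as a period. However, SAP 2.1.5.1 defines treatment-emergent hypoglycaemia as events in the on-treatment period.

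**The concern.** A rate needs the same window above and below the line. Here the numerator can pick up events on the calendar day after the last injection, while the denominator leaves that day out. This applies to participants with complete dates as well as to those with missing ones.

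The same subsection also describes person-time for one endpoint in different terms: days exposed for the crude rate, the treatment-emergent period for the model, and patient-years of exposure for the rate of severe events with neuroglycopenic symptoms or low SMPG. None is defined where it is used. Two programmers could build different denominators, and the tabulated rates would not be reproducible from the model's own person-time. What is at stake is the accuracy and traceability of a descriptive secondary figure, not a between-arm conclusion.

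**Working it through.** The documents state no hypoglycaemia rate or event count, so there is no plan figure to reproduce. The check compares the two windows.

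**Inputs**
- Denominator, L = last date − first date + 1 (SAP 2.4.3.1).
- Event window in calendar days = last date − first date + 2 = L + 1 (SAP 2.1.5, with the day after the last injection included).
- Planned treatment: 16 weeks = 112 days. With the COVID-19 extension in SAP 1.4: up to about 24 weeks = 168 days.
- Assumptions: constant event rate and full capture of events on the extra day.

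**Step 1: one participant.** Maximum excess = (L + 1)/L − 1.

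| Days of IMP (L) | Event window | Maximum excess |
|---|---|---|
| 84 | 85 | 1.19% |
| 112 | 113 | 0.89% |
| 168 | 169 | 0.60% |

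For illustration, an assumed true rate of 50 events per patient-year would be tabulated as 50 × 113/112 = 50.45.

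**Step 2: one arm.** The SAP rate pools total episodes over total days, so the arm-level excess is 1 divided by mean exposure. The early-stopping patterns below are assumed.

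| Pattern in the arm | Mean exposure (days) | Excess |
|---|---|---|
| 10% stop at day 28 | 0.9 × 112 + 0.1 × 28 = 103.6 | 0.97% |
| 20% stop at day 28 | 0.8 × 112 + 0.2 × 28 = 95.2 | 1.05% |
| 20% stop at day 14 | 0.8 × 112 + 0.2 × 14 = 92.4 | 1.08% |

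**Step 3: ratio of the two crude rates.** With mean exposures a and b, the mismatch multiplies the ratio by [(a + 1)/a] / [(b + 1)/b]. This gives 1.0000 for 112 v 112 days, 0.9994 for 112 v 105 and 0.9971 for 112 v 84. Setting each pattern in Step 2 against a 112-day arm moves the ratio by less than 0.2%.

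**Step 4: sensitivity to how the window is read.** If the clock starts at an assumed 08:00 first injection on Day 1 and runs to the end of the day after the last injection, the excess is 16/24 = 0.67 day, or 0.67/112 = 0.60%. If the window ends exactly 24 hours after the last injection, its length is (last − first) + 1 day. That equals L, and the excess is 0%.

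**The case against.** The strongest reply is that the protocol's wording can be read in clock time. On that reading the on-treatment period is exactly as long as the exposure formula and nothing is mismatched. This does not rescue the SAP, which sets out the detailed analysis and works in calendar days: the day after the last injection is expressly included, and post-treatment begins the day after that.

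Other points on that side stand, at least in part:

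- **The terms are inferred.** The hypoglycaemia section neither defines days exposed nor refers back to 2.4.3.1, and the treatment-emergent period is never defined. The difference in person-time is the natural reading rather than an explicit statement.
- **Capture on the extra day is uncertain.** The Schedule of Activities has hypoglycaemia recorded throughout the study and a contact at Week 16 plus 1 day. It marks SMPG and diary review only through Visit 7. With partial capture the excess is smaller, and the longer denominator would then err slightly low.
- **Exact agreement is not expected anyway.** The Poisson model adjusts for the HbA1c stratum, so crude and modelled results would differ somewhat even with identical person-time.

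A reader might infer that every crude rate must be too high. The documents do not support that, because a category with no events on the extra day is not inflated. A reader might also take the ratio for a very early stopper, such as 8/7 (14%) at 7 days or 29/28 (3.6%) at 28 days, as the bias. The rate is pooled over all participants, so such a person adds only a few days to a large sum. The arm-level figure stays near 1%.

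**Conclusion.** The mismatch is present in the SAP as written. Crude hypoglycaemia rates are expected to be slightly too high: at most about 0.9% for a 112-day completer, and about 1% for an arm under the early-stopping patterns assumed above. These sizes rest on the SAP's calendar-day wording, on reading days exposed as the SAP's exposure duration, on an even event rate and on full capture on the extra day.

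It would be wrong to infer that the treatment comparison is biased. Both arms shift in the same direction. On the natural reading, the modelled rate ratio uses the window that matches its events and is unaffected. Both documents call the safety analyses descriptive, and no conclusion would change. This is a definition to tidy up, at the lowest severity.

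**What to change.** In SAP 2.4.5.1, define one on-treatment duration as last injection date minus first injection date plus 2 calendar days. Use it both as the crude-rate denominator and, on the log scale, as the Poisson offset. State that the treatment-emergent period means this duration, and apply it to the other per-patient-year rate in the same section. Keep the 2.4.3.1 duration for the exposure tables only.

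Record the change in the SAP as a clarification of the denominator in protocol Table 7. Protocol 9.4 provides for changes to planned analyses to be addressed in the SAP, so a protocol amendment should not be needed for this alone.

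The cost is a short SAP edit and one derived variable that the model needs in any case. Data collection, enrolment and design are untouched.

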#### ***2.4.5.2 Analyses of adverse events***

##### ***Generalities***

The primary focus of adverse event reporting will be on treatment-emergent adverse events. Pretreatment and posttreatment adverse events will be described separately.

If an adverse event date/time of onset (occurrence, worsening, or becoming serious) is incomplete, an imputation algorithm will be used to classify the adverse event as pretreatment, treatment-emergent, or posttreatment. The algorithm for imputing date/time of onset will be conservative and will classify an adverse event as treatment emergent unless there is definitive information to determine it is pretreatment or posttreatment. Details on classification of adverse events with missing or partial onset dates are provided in [Section 2.5.1](#).

Adverse event incidence tables will present by SOC and/or PT, the number (n) and percentage (%) of patients experiencing an adverse event. Multiple occurrences of the same event in the same patient will be counted only once in the tables within a treatment phase. The denominator for computation of percentages is the safety population within each treatment group.

Sorting within tables ensures the same presentation for the set of all adverse events within the observation period (pretreatment, treatment-emergent, and posttreatment). For that purpose, the table of all treatment-emergent adverse events presented by SOC and PT sorted by the internationally agreed SOC order and decreasing frequency of PTs within SOCs will define the presentation order for all other tables unless otherwise specified. Sorting will be based on results for the switching arm.

Analyses of all TEAE(s) will be generated for the safety population.

#### ***Analysis of all TEAE(s)***

- Overview of TEAEs, summarizing number (%) of patients with any
  - TEAEs,
  - Serious TEAEs,
  - TEAEs leading to death,
  - TEAEs leading to permanent treatment discontinuation.
- Number (%) of patients experiencing TEAE(s) presented by PT, sorted by decreasing incidence of PT in the switching group.
- All TEAEs by primary SOC and PT, showing number (%) of patients with at least one TEAE, sorted by SOC internationally agreed order and decreasing incidence of PT in the switching group within SOC. This sorting order will be applied to all other tables, unless otherwise specified. If the number of patients impacted by COVID-19 is sufficient, TEAEs will also be presented by subgroup of COVID-19 impact (Non-impacted, Impacted) (see definition [Section 2.2](#)).
- All TEAEs regardless of relationship and related to IMP by primary SOC and PT, showing number (%) of patients with at least one TEAE, sorted by the sorting order defined above.
- All TEAEs by maximal severity, presented by primary SOC and PT, showing number (%) of patients with at least one TEAE by severity (ie, mild, moderate, or severe), sorted by the sorting order defined above.

#### ***Analysis of all treatment-emergent SAE(s)***

- All treatment-emergent serious adverse events regardless of relationship and related to IMP, by primary SOC and PT, showing number (%) of patients with at least 1 serious TEAE, sorted by SOC internationally agreed order and decreasing incidence of PTs according to all TEAE summary within SOC.

#### ***Analysis of all TEAE(s) leading to treatment discontinuation***

- All treatment-emergent adverse events leading to permanent IMP discontinuation, by primary SOC and PT, showing the number (%) of patients sorted by the internationally agreed SOC order and decreasing incidence of PTs according to all TEAE summary within SOC.

### ***Analysis of all TEAE(s) requiring specific monitoring***

- All TEAE(s) related to injection site reactions, hypersensitivity reactions, or events confirmed as allergic reactions by ARAC regardless of relationship and related to IMP by PT, showing number (%) of patients sorted by decreasing incidence of PT based on results for the switching group.
- The number of events sent for adjudication to the ARAC and the number (%) of events positively adjudicated as allergic reaction or not by the ARAC will be summarized for each treatment group.
- A listing of all events adjudicated by ARAC will be provided with the result of ARAC adjudication.

### ***Analysis of adverse events of special interest***

- Number (%) of patients experiencing AESI presented by categories described in [Section 2.1.5.2](#).

### ***Analysis of pretreatment and posttreatment adverse events***

- Depending on the number, a listing or a table of all pre-treatment and post-treatment AEs will be provided.

### ***Analysis of TEAEs related to COVID-19***

All TEAEs related to COVID-19 by primary SOC and PT, showing the number (%) of patients with at least one TEAE related to COVID-19, sorted by the internationally agreed SOC order and decreasing incidence of PTs according to all TEAE summary within SOC. TEAEs related to COVID-19 will be identified using a CMQ (customized MedDRA queries) list.

#### ***2.4.5.3 Deaths***

The following deaths summaries will be generated on the safety population.

- Number (%) of patients who died by study period (on-study, on-treatment and reasons for death).
- All TEAEs leading to death (death as an outcome on the adverse event e-CRF page as reported by the investigator), by primary SOC and PT, showing number (%) of patients sorted by SOC internationally agreed order and decreasing incidence of PTs according to all TEAE summary within SOC.
- A listing of all deaths.

#### ***2.4.5.4 Analyses of laboratory variables***

The summary statistics (including number, mean, median, standard deviation, minimum, and maximum) of all laboratory variables (central laboratory values and changes from baseline) will be calculated for each visit or study assessment (baseline, Week 16, and last on-treatment value)

by treatment group. This section will be organized by biological function as specified in [Section 2.1.5.4](#).

The incidence of PCSAs (list provided in [Appendix A](#)) at any time during the on-treatment period will be summarized by biological function and treatment group whatever the baseline level and according to the following baseline status categories:

- Normal/missing,
- Abnormal according to PCSA criterion or criteria.

For parameters for which no PCSA criteria are defined, similar table(s) using the normal range will be provided.

#### ***Drug-induced liver injury***

The liver function tests, namely AST, ALT, alkaline phosphatase, and total bilirubin, are used to assess possible drug-induced liver toxicity. The proportion of patients with PCSA values at any post-baseline visit by baseline status will be displayed by treatment for each parameter.

A graph of distribution of peak values of ALT versus peak values of total bilirubin will also be presented. Note that the ALT and total bilirubin values are presented on a logarithmic scale. The graph will be divided into 4 quadrants with a vertical line corresponding to  $3 \times \text{ULN}$  for ALT and a horizontal line corresponding to  $2 \times \text{ULN}$  for total bilirubin.

Listing of possible Hy's law cases identified by treatment (eg, patients with any elevated  $\text{ALT} > 3 \times \text{ULN}$ , and associated with an increase in bilirubin  $> 2 \times \text{ULN}$ ) will be provided with ALT, AST, alkaline phosphatase, total bilirubin, and the following complementary parameters (if available): conjugated bilirubin and prothrombin time/international normalized ratio (INR), creatine phosphokinase (CPK), serum creatinine and complete blood count.

#### ***2.4.5.5 Analyses of vital sign variables***

The summary statistics (including number, mean, median, standard deviation, minimum, and maximum) of all vital signs variables (raw values and changes from baseline) described in [Section 2.1.5.5](#) including body weight, will be calculated for each visit or study assessment (baseline, Week 16, last on-treatment value) by treatment group.

The incidence of PCSAs at any time during the on-treatment period will be summarized by treatment irrespective of the baseline level.

#### ***2.4.5.6 Analyses of electrocardiogram variables***

Not applicable.

## 2.4.6 Analyses of anti-insulin aspart antibody data

### 2.4.6.1 Analyses of anti-insulin aspart antibody data

The analyses of immunogenicity data will be descriptive (no formal statistical testing) and based on the AIA population.

